- Evaluate safety at the dose(s) used to assess imaging feasibility and select the dose(s) and imaging schedule(s) postdose that are safe and provide optimal imaging of solid tumors and metastatic lymph nodes; the dose and time postdose chosen for the detection of primary tumors and metastatic lymph nodes may be the same or different

Part 2 Primary Objective:

Verify the safety and diagnostic performance of ONM-100 compared to standard pathology at the dose(s) and imaging schedule(s) postdose selected from Part 1 for the detection of the primary tumors and the metastatic lymph nodes in a variety of solid cancers (which may include

Part 1 and Part 2 Secondary Objective

Evaluate the PK profile of ONM-100 at the dose(s) and imaging schedule(s) postdose used to assess
optimal imaging in Part 1 and Part 2

Part 3 Objective:

 To assess the safety and efficacy (sensitivity and positive predictive value [PPV]) of ONM-100 at a dose of 1 mg/kg for intraoperative imaging during head and neck squamous cell carcinoma (HNSCC) surgery, administered at 24 ±8 hours prior to surgery.

Part 3 Primary Endpoints:

- Sensitivity: True Positive Biopsies / (True Positive + False Negative Biopsies)
- PPV: True Positive Biopsies / Tumor Positive Biopsies + False Positive Biopsies

Part 3 Secondary Endpoints:

- Proportion of patients with at least one clinically significant event identified during surgery (occult disease detected, positive margin)
- Number of margins identified by ONM-100 and NIR imaging that could not be observed with white light and palpation alone
- Detection rate of HNSCC between ONM-100 fluorescence at time of surgery versus frozen sections determined by final pathology report
- Detection of positive margins at time of surgery that triggers subsequent biopsy
- Re-resection rate

Part 3 Exploratory Endpoints:

Study Design:

This is a non-randomized, open-label, multi-center, safety, PK, and imaging feasibility study of ONM-100, an intraoperative fluorescence imaging agent. The study consists of 3 parts (Parts 1, 2 and 3).

Part 1 will be performed in a dose-escalation design (maximum of 5 cohorts of 3 patients each) to
determine the dose(s) at which ONM-100 fluorescence can be used to image metastatic lymph nodes
and primary tumors in patients with HNSCC and breast cancer undergoing routine surgery at 3 ±2
hours, and if needed at an alternate imaging schedule postdose.

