Surgical specimens obtained during the routine surgery and any ONM-100 fluorescence guided biopsies will be prepared using standard specimen processing methods and timelines. Specimens will be sampled and analyzed according to routine pathologic evaluation.

After surgery, the patient will be strictly observed following the standard, respective, postoperative protocol. Patients will be monitored for safety assessments and sample procurement.

Medical history, prior medication use, hemoglobin, and Karnofsky performance status will be evaluated at Screening and pretreatment on Day 0. Pregnancy tests will be performed at Screening and at Day 28 (\pm 5 days). Electrocardiograms (ECGs) will be performed pretreatment, at 30 \pm 10 minutes postdose on Day 0 and Day 10 (\pm 5 days).

Patient safety will be assessed for 28 days (\pm 5 days). All patients will be monitored for vital signs and physical examination pretreatment and at various time points up to Day 10 (\pm 5 days). All patients will be monitored for comprehensive metabolic panel (CMP) and complete blood count (CBC) with differentials pretreatment and at various time points up to Day 28 (\pm 5 days). All patients will be monitored for treatment-emergent adverse events (TEAEs) and concomitant medication use from the start of dosing up to Day 28 (\pm 5 days). TEAEs will be followed closely during the study to identify any potential DLTs.

Number of Patients

Up to 60 patients will be enrolled in this study (with planned allocation of up to 15 patients in up to 5 cohorts in Part 1, approximately 10 to 20 patients in Part 2, and approximately 20 to 30 patients in Part 3). The actual number of patients in Part 1 and Part 2 may vary, depending on the number of Part 1 cohorts and Part 2 Groups/tumor types that are activated for enrollment.

All patients will receive a single dose of ONM-100 followed by routine surgery and pathology of the respective solid cancer. Based on the ON-1001 study experience, we estimate that 3 patients for each dose is sufficient for safety and imaging feasibility evaluations in Part 1. Each patient's tumors will be imaged intraoperatively and at planned sites post operatively. For those patients with fluorescence in the surgical wound bed after standard procedures, tissue biopsy may be taken at surgeon's or pathologist's discretion. Up to 3 additional patients may be enrolled in the event of a DLT.

Inclusion Criteria

Patients must meet the following inclusion criteria:

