abnormal laboratory findings that are considered at least possibly related to ONM-100 will be followed until resolved or stabilized.

Criteria for Evaluation

Efficacy Analyses

In Part 1 and Part 2, ONM-100 fluorescence from in vivo and excised tissues will be imaged using intraoperative and post-operative NIR cameras and will be correlated with the histopathological confirmation of tumor and normal tissues to determine ONM-100's diagnostic performance.

In Part 3, the intraoperative fluorescence status of collected primary tumor, SOC and ONM-100 guided biopsies, as well as lymph nodes will be compared to histological analyses of the collected specimens.

Safety Analyses

Safety assessments will include the following safety related parameters:

- TEAE incidence, severity, and relationship to study drug
- Physical examination
- Vital signs
- ECGs
- Clinical laboratory (CMP, hemoglobin, and CBC with differentials)

Pharmacokinetic Analyses

Characterization of the ONM-100 PK profile will include the following major PK parameters:

- Maximum plasma concentration (C_{max})
- Time to C_{max} (T_{max})
- Area under the time-concentration curve (AUC)
- Total body clearance (CL)
- Volume of distribution (Vz)
- Volume of distribution at steady state (Vss)
- Elimination rate constant (λz)
- Terminal elimination half-life (t_{1/2})

Statistical Methods

This is a pilot study with the intention of gathering data to assess feasibility and imaging metrics for the efficacy analysis. Therefore, no formal statistical hypothesis testing will be performed for making development decisions.

Analysis populations

- Safety Population: all patients who receive any dose of ONM-100
- Efficacy Population: all patients who received any dose of ONM-100 and who have sufficient imaging and pathology analysis data to calculate fluorescence intensity and pathology correlation for ≥1 tumor sample
- Pharmacokinetic Population: all patients who receive ONM-100 and who have sufficient ONM-100
 plasma concentration data to calculate ≥1 PK parameter.

Sample Size Calculation

Given the exploratory nature of the study, formal sample size calculations were not performed.

Protocol Amendment 6.0

Safety Analyses

The safety analyses will be in the Safety Population.

Adverse events (AEs), vital signs, ECGs, and conventional clinical laboratory data (CMP and CBC with differentials) will be summarized using descriptive statistics.

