6.3 Measures Taken to Minimize Bias

Randomization, treatment allocation, and blinding are not applicable since this is a single-arm, singledose, open-label study. However, surgeons will be blinded to the presence or absence of fluorescence during standard of care surgery. Also, all pathology analyses will be blinded to the presence or absence of fluorescence, including surgical bed biopsies, tumor specimens, lymph nodes, lymph node bundles, bread loaf slices, and formalin-fixed and paraffin-embedded (FFPE) blocks.

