10.3 Pathologic Assessments

Tumor specimens will be processed for histology according to the routine pathology practice used in clinical cancer care. If an ONM-100 fluorescence tissue is not selected by routine pathological sampling, select additional samples from the fluorescence tissue for pathological correlations. As needed, an independent central pathology reading will be used for pathology assessments when data required for analysis are not provided in the standard of care report.

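### The Part 3 PPV is counted in biopsies, while the only legible rule leaves biopsy of residual wound-bed fluorescence to discretion; unbiopsied foci would drop out and could inflate the PPV

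*Protocol*

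**What the plan says.** All of the following is in the Protocol.

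- **Endpoints (Section 1.0, Part 3 Primary Endpoints).** Both primary efficacy measures use the biopsy as unit: "Sensitivity: True Positive Biopsies / (True Positive + False Negative Biopsies") and "PPV: True Positive Biopsies / Tumor Positive Biopsies + False Positive Biopsies". The second is printed without brackets and with a different first term in the denominator. I read it as true positives over true plus false positives; the wording is a separate matter.
- **What is compared (Section 1.0, Criteria for Evaluation, Efficacy Analyses).** The Part 3 comparison reads: "the intraoperative fluorescence status of collected primary tumor, SOC and ONM-100 guided biopsies, as well as lymph nodes will be compared to histological analyses". Only collected specimens enter.
- **When residual fluorescence is biopsied (Section 1.0, Number of Patients).** For patients with "fluorescence in the surgical wound bed after standard procedures, tissue biopsy may be taken at surgeon's or pathologist's discretion". The paragraph opens with "All patients will receive a single dose of ONM-100 followed by routine surgery and pathology of the respective solid cancer", and the section counts the 20 to 30 Part 3 patients.
- **Neighbouring rules.** Section 6.3 says that "surgeons will be blinded to the presence or absence of fluorescence during standard of care surgery". Section 10.3 says "If an ONM-100 fluorescence tissue is not selected by routine pathological sampling, select additional samples from the fluorescence tissue for pathological correlations". Section 11.8 plans a complete case analysis, with a sensitivity analysis for missing data.
- **What cannot be read.** The Part 3 imaging and biopsy steps in Sections 1.0, 6.1 and 9.1.4.1 are largely blacked out.

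**The concern.** PPV should say how often a fluorescent signal is tumour. If a clinician chooses which fluorescent foci are biopsied, the computed figure says how often a signal that was also thought worth sampling is tumour. This is partial verification of test-positives, and some of the clinician's judgement is credited to the agent. It is distinct from any effect of guided biopsies on sensitivity.

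The neighbouring rules do not close the gap. Blinding of surgeons covers standard of care surgery, and the wound-bed decision comes after it, with the fluorescence in view. The extra-sampling rule in Section 10.3 concerns tissue missed by routine pathological sampling, which is tissue already excised. A sensitivity analysis for missing data cannot count foci that were never recorded.

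The wound bed also matters for the claim of added value: the Part 3 secondary endpoints include occult disease and margins not observed with white light and palpation.

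**Working it through.** The protocol states no PPV target, precision or biopsy rate, so there is no figure of its own to reproduce. Every rate and share below is an assumption.

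**Notation.** p = true PPV over all fluorescent wound-bed foci; s1 and s0 = probability that a tumour-bearing or a benign fluorescent focus is biopsied; w = share of wound-bed foci among all fluorescent specimens; q = PPV in the other fluorescent specimens, which are collected regardless.

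**Step 1, wound-bed foci alone.** Observed PPV = p·s1 / [p·s1 + (1−p)·s0].

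| p | s1 | s0 | Calculation | Observed |
|---|---|---|---|---|
| 0.50 | 0.95 | 0.50 | 0.475/0.725 | 0.655 |
| 0.30 | 0.95 | 0.50 | 0.285/0.635 | 0.449 |
| 0.50 | 0.95 | 0.80 | 0.475/0.875 | 0.543 |
| 0.70 | 0.50 | 0.90 | 0.350/0.620 | 0.565 |

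With s1 = s0 the observed value equals p. The bias is upward only when s1 > s0; the last row shows the reverse.

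**Step 2, pooled over all fluorescent specimens.** True PPV = (1−w)q + wp. Observed PPV = [(1−w)q + w·p·s1] / [(1−w) + w·p·s1 + w(1−p)s0]. Take q = 0.9.

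| w | p | s1 / s0 | True | Observed | Shift (points) |
|---|---|---|---|---|---|
| 0.10 | 0.5 | 0.95 / 0.50 | 0.860 | 0.8575/0.9725 = 0.882 | +2.2 |
| 0.25 | 0.5 | 0.95 / 0.50 | 0.800 | 0.79375/0.93125 = 0.852 | +5.2 |
| 0.10 | 0.4 | 1.00 / 0.50 | 0.850 | 0.850/0.970 = 0.876 | +2.6 |
| 0.10 | 0.2 | 1.00 / 0.50 | 0.830 | 0.830/0.960 = 0.865 | +3.5 |
| 0.25 | 0.4 | 1.00 / 0.50 | 0.775 | 0.775/0.925 = 0.838 | +6.3 |
| 0.25 | 0.2 | 1.00 / 0.50 | 0.725 | 0.725/0.900 = 0.806 | +8.1 |

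**Step 3, what a lower bound shows.** Suppose 40 fluorescent wound-bed foci, 20 with tumour, of which 19 tumour-bearing and 10 benign are biopsied. The reported PPV is 19/29 = 65.5%. Counting the 11 unbiopsied foci as false positives gives 19/40 = 47.5%. The true value is 20/40 = 50%, and the verified fraction is 29/40 = 72.5%. The two PPV figures bracket the truth here, and the lower one cannot be computed unless the 11 foci were recorded.

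**The case against.** The strongest objection is that Part 3's own biopsy rule may stand in text we cannot read. The Part 3 description in the Synopsis breaks off just where guided biopsy would follow standard of care margins, and a secondary endpoint speaks of positive margins that trigger a biopsy. The discretion sentence sits in a paragraph on patient numbers, next to dose-escalation content, and may have been carried over from Parts 1 and 2. This stands as a limit on the conclusion. It does not remove the point: the sentence is not restricted to a part, and a mandatory rule elsewhere would contradict it and need reconciling.

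Second, the direction is not given by the document. Discretion might follow anatomical risk, which need not track histology, and tissue that looked suspicious should largely have been resected already. This also stands: upward bias is the expected direction, not a certainty.

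Third, this is a pilot with descriptive analysis and no PPV target, and a sensitivity analysis belongs in an SAP. With no test planned, however, the point estimate is the result, and selection bias does not shrink with more patients. An SAP can define a bound but cannot recover unrecorded foci. Sections 6.1 and 9.1.4.1 do require all fluorescence images to be saved, so part of the record may exist; no legible text links each focus to a biopsy decision or to a reason for none.

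**Conclusion.** The concern holds conditionally. On the legible text, unbiopsied fluorescent wound-bed foci fall out of a primary endpoint, and the PPV is inflated if benign-looking foci are skipped more often than tumour-bearing ones. Under the stated assumptions this is about +2 to +8 points on a pooled PPV for wound-bed shares of 10% to 25%, and about +16 points (50% read as 66%) on a wound-bed PPV alone.

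A reader might infer two stronger claims that the documents do not support. One is that the Part 3 PPV is certainly biased upward: the Part 3 procedures are partly unreadable, and the direction depends on biopsy rates that the protocol does not give. The other is that the primary PPV would be off by 15 points or more. That size applies to wound-bed foci only, because primary tumour, standard of care and lymph node specimens also enter the comparison and dilute the effect.

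**What to change.** 1. State whether the discretion sentence in the Synopsis governs Part 3, and reconcile it with the Part 3 procedures. No biopsy beyond those already planned is asked for.
2. Have the technician or physician assistant who already takes the images log each fluorescent wound-bed focus (site, image number) before the biopsy decision, and record the reason when no biopsy is taken.
3. Report the fraction of fluorescent foci with histology. Give the wound-bed and overall PPV, each beside a lower bound that counts unbiopsied fluorescent foci as false positives. The analysis detail can sit in the SAP; the log has to be in place before surgery.

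The cost is one case report form page, a few table lines, and a less favourable figure printed beside the headline PPV.

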4.2.1.5 Fluorescence Imaging Data

Histology confirmed tumor and normal tissue specimens showed clear demarcation (no overlap) of mean fluorescence intensity (MFI) for each patient (n=15) when plotted against each patient's plasma concentration at 10 minutes. Tumor fluorescence increased with increasing initial plasma concentration (Figure 8).

C10 = ONM-100 concentration at 10 minutes

Postoperative ex-vivo mean fluorescence intensity of the histology confirmed tumor (red dots) and normal (black dots) tissues for the pathologist selected bread loaf slice specimens for each patient versus plasma C₁₀.

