7.1 Patient Inclusion Criteria

Patients must meet ALL of the following inclusion criteria to be enrolled:

- 1. Adults ≥ 18 years of age
- 2. Biopsy-confirmed diagnosis for primary or recurrent disease (or high clinical suspicion in the opinion of the Investigator)
 - a. Part 1: Stage 0 to 4
 - b. Part 2:
 - Stage 0 to 4
 - Stage 2 to 4
 - c. Part 3:

Stage 2 to 4

- 3. Acceptable hematologic status (as respective standard surgery protocol requires, as determined by the Investigator), kidney function, and liver function. Elevations of creatinine, ALT, AST, alkaline phosphatase [AP], or total bilirubin ≥1.5× upper limit of normal (ULN) must be determined to be not clinically significant by the Investigator and approved by the Medical Monitor.
- 4. Documented negative serum pregnancy test for women of childbearing potential (ie, premenopausal women with intact reproductive organs and women <2 years after menopause)
- 5. Male patients and female patients of child-bearing potential (ie, premenopausal women with intact reproductive organs and women <2 years after menopause) must agree to and comply with using medically acceptable contraception including surgical sterilization (eg, hysterectomy, bilateral oophorectomy, bilateral tubal ligation), intrauterine device, oral contraceptive, contraceptive patch, long acting injectable contraceptive, partner's vasectomy, double-barrier method (condom or diaphragm plus spermicide or condom plus diaphragm), or abstinence during the trial and for 6 months thereafter.

- 6. Agree to abstain from alcohol consumption
- 7. Adequate potential for follow up

8. Willing and able to provide written informed consent

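### Does an Efficacy Population keyed to fluorescence intensity in a tumor sample distort the Part 3 sensitivity and PPV?

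*Protocol*

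**What the plan says.** Under Analysis populations, the Protocol Synopsis admits to the Efficacy Population any dosed patient "who have sufficient imaging and pathology analysis data to calculate fluorescence intensity and pathology correlation for ≥1 tumor sample". This one definition serves Parts 1, 2 and 3.

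Under Efficacy Analyses, the synopsis says of the Part 3 comparison that "the intraoperative fluorescence status of collected primary tumor, SOC and ONM-100 guided biopsies, as well as lymph nodes will be compared to histological analyses". The Part 3 primary endpoints are biopsy-level sensitivity and PPV, the latter printed as "PPV: True Positive Biopsies / Tumor Positive Biopsies + False Positive Biopsies". The evident intent is true positives over true plus false positives, and that is used below. One secondary endpoint is counted per patient: "Proportion of patients with at least one clinically significant event identified during surgery".

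Section 7.1 requires a biopsy-confirmed diagnosis "or high clinical suspicion in the opinion of the Investigator", so a dosed patient whose final histology shows no tumour is possible. Section 11.2 announces the population definitions, but they do not appear in the public copy. Appendix 3, to which Sections 11.0 and 11.4 send the reader for outcome assessment, is also not available.

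**The concern.** Two things invite criticism.

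**Intensity against status.** The population rule asks for a calculable intensity. The Part 3 endpoints need only a positive or negative fluorescence status and a histology result for each biopsy. Read literally, a Part 3 patient with status and histology on every biopsy but no intensity value would be left out.

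**Meaning of tumor sample.** If the term means histology-confirmed tumour, a patient enrolled on suspicion whose histology is benign falls outside the population. That patient can contribute false-positive or true-negative biopsies, but no true positives or false negatives. Removing such patients can only raise PPV or leave it unchanged. The per-patient secondary endpoint would likewise lose only patients who cannot have the event.

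At stake is the reported value of a Part 3 primary endpoint. The study plans no formal hypothesis test, so there is no error rate to protect. The harm would be to the estimate.

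**Working it through.** The protocol gives no sample size calculation or expected performance, so there is no planned figure to reproduce. The check has three steps.

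**1. Size of the effect if a tumor sample must be confirmed tumour.**
From the documents: N = 20 to 30 in Part 3 (Synopsis, Study Design). Assumed, because the documents give no counts: each tumour patient yields *t* true-positive and *f* false-positive biopsies, and each of *k* benign patients yields *g* false positives.

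- PPV in all dosed patients = (N − k)t / [(N − k)(t + f) + kg]
- PPV after exclusion = t / (t + f)

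The extremes over four assumed sets, (t, f, g) = (1, 0.25, 1), (2, 0.5, 1), (3, 0.5, 2) and (1, 0.5, 2), are:

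| N | k | t, f, g | PPV, all | PPV, excluded | Difference |
|---|---|---|---|---|---|
| 30 | 1 | 2, 0.5, 1 | 58/73.5 = 0.789 | 0.800 | 1.1 points |
| 20 | 1 | 1, 0.5, 2 | 19/30.5 = 0.623 | 0.667 | 4.4 points |
| 30 | 2 | 2, 0.5, 1 | 56/72 = 0.778 | 0.800 | 2.2 points |
| 20 | 2 | 1, 0.5, 2 | 18/31 = 0.581 | 0.667 | 8.6 points |

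With k = 0 the difference is zero. By this route sensitivity does not move, because a benign patient has no true positives or false negatives.

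For the per-patient endpoint, with an assumed 10 events and 3 benign patients dropped from 30: 10/30 = 33.3% against 10/27 = 37.0%.

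The chance of at least one benign patient is 1 − (1 − p)^N. At an assumed p of 1% it is 18% (N = 20) to 26% (N = 30). At 5% it is 64% to 79%. The documents do not give p. Stage 2 to 4 entry for Part 3, and the exclusion in Section 7.2 of patients diagnosed by excisional biopsy, both point to a low value.

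**2. Which reading the text supports.**
- The Part 3 paragraph of the synopsis has the whole tumor specimen imaged with the intraoperative camera, before any histology exists.
- Section 6.3 blinds the pathology reading of tumor specimens to fluorescence, so the term is in use before the result is known.
- Section 10.3 states: "Tumor specimens will be processed for histology according to the routine pathology practice".
- Section 4.2.1.5, where confirmed tissue is meant, says so: "Histology confirmed tumor and normal tissue specimens showed clear demarcation".

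The population rule also asks for a correlation with pathology, which fits a sample whose histology is still to be compared. On this reading a benign patient with an imaged and examined specimen stays in, and every difference in step 1 becomes zero.

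**3. Whether the intensity requirement drops anyone.**
Part 3 plans imaging of the whole tumor specimen and the excised margins. Sections 6.1 and 9.1.4.1 have all Part 3 fluorescence images saved. The rule asks for sufficient data to calculate an intensity for a single sample, and a saved image of the main specimen would ordinarily supply that. A patient with status on biopsies or nodes only would need a departure from planned imaging. Each such patient would be 1/30 = 3.3% to 1/20 = 5.0% of Part 3. By this route the direction is unknown, because any type of biopsy could be lost and sensitivity could move too.

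**The case for a change.** The strongest argument for a change is that the protocol does not leave the population to the analysis plan. It fixes a definition, and that definition suits the correlation analysis of Parts 1 and 2 better than the counts of Part 3. Section 9.1.4.3 points the same way: storage of quantitative fluorescence data is listed for Parts 1 and 2 and does not appear in the visible Part 3 text. An analysis plan that copies the rule inherits the mismatch. Rewording would take one sentence and no new data, and in so small a study a few points of PPV would be visible.

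The wording mismatch stands. The rest carries less weight. The visible Part 3 procedures are heavily redacted, so silence about quantitative data there proves little. That the term is undefined, or that no population is named for PPV, cannot be established while the Section 11.2 definitions, much of Section 11.4 and Appendix 3 are not visible. The PPV shift needs four conditions together: the less natural reading, PPV computed in this population, a dosed patient with benign histology, and false-positive biopsies in that patient. Section 11.8 also provides a sensitivity analysis for missing data.

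**Conclusion.** No change is needed. The synopsis definition is worded for Parts 1 and 2 and carried over to Part 3. An analyst would sensibly treat a Part 3 patient as evaluable when at least one specimen has both a fluorescence result and a histology result, whatever the histology shows. Applied to the planned procedures, the rule as written should admit essentially the same patients, so no change in sensitivity, PPV or the per-patient proportion has been shown.

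This rests on two assumptions: that a tumor sample means tissue taken as tumour and not yet read, as the protocol's other usage indicates, and that the planned specimen imaging is carried out. If the first fails, PPV would be overstated by about 1 to 4 points for one benign patient with false positives and 2 to 9 points for two, under assumed biopsy counts. If there is no such patient, the overstatement is zero. Because the study is a descriptive pilot, even that would affect a reported estimate and not a formal decision.
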